C.7. Genotyping: Genotyping for urn randomization will be done using Cells-to-Ct assay reagent (Applied Biosystems, Inc) to allow rapid genotyping at the *AKR1C3* rs12529 SNP directly from blood. TaqMan allelic discrimination assays have been designed and used previously by our group for the rs12529 polymorphism in the *AKR1C3* gene that we identified to be associated with alcohol dependence (Milivojevic et al. 2011) and with heavy drinking in college students (Milivojevic in preparation). The anticipated genotype distribution frequency based on a sample of 531 AD subjects is GG 0.13; GC 0.49; CC 0.38. Reference DNA samples with each of the three possible genotypes at rs12529 will be included with each subject sample. Additional DNA will be purified from whole blood using the PureGene kit (GentraSystems, Minneapolis, MN) to allow confirmation of initial rapid genotyping for urn randomization using batched purified DNA samples. Secondary analysis will examine whether polymorphisms in the genes (*SRD5A1* and *SRD5A2*) encoding the enzyme 5 α -reductase type 1 and 2 which are the targets of dutasteride or other neuroactive steroid metabolic genes might also moderate treatment response. Polymorphisms in GABA(A) subunit genes will be considered as potential moderators of treatment outcome as neuroactive steroids act via GABA(A) receptors and we have previously reported that a polymorphism in *GABRA2* was associated with treatment response in the Project MATCH alcohol study (Bauer et al., 2007). Secondary analysis for Aim 4 will examine genetic variations in the genes *SLC6A4*, *NPY* and *FKBP5* that we have found to moderate stress related drinking among college students (Covault et al, 2007; and unpublished data). With continued advances in knowledge during the time of this study we anticipate that DNA will also be used to examine genotypes at other candidate markers related to alcohol use and related behaviors.

C.8. Data Analysis:

C.8.a.1. Safety: Safety will be analyzed using categorical outcomes, defined by the type and severity of adverse effects. Summary measures of adverse events (AEs) will be developed by organ system from the adverse event checklist and will be compared for patients receiving dutasteride or placebo using χ^2 analysis. Comparisons will be conducted on 1) the number of patients in each of the two groups who report AEs, 2) the number of patients in each of the two groups who report moderate-to-severe AEs, and 3) the number of patients in each group who discontinue treatment due to AEs. Individual AEs that occur in $\geq 5\%$ of patients in either medication condition will be examined using χ^2 analysis.

C.8.a.2. Efficacy: An important initial consideration will be to identify baseline differences between groups that may have occurred despite the use of urn randomization. The distribution of outcome data will also be examined prior to analysis, to determine the need for transformation and whether parametric analytic methods can be utilized. Successful outcome will be defined in terms of three primary dependent measures: SDs/week, HDDs/week, % of subjects with no HDDs, and % of subjects with non-hazardous drinking (no HDDs and SDs/week <15). Patients will be followed irrespective of whether they continue to receive treatment, so that analysis of both primary drinking measures and secondary outcomes will include all data available for the 12-week treatment period. Data for analyses of drinking outcomes during the 12-week treatment period will come from the daily IVR reports (missing IVR report days which will be coded as the larger of either 5 standard drinks (i.e. a HDD) or the IVR average daily use for the week reporting interval). Analysis of drinking for the 6-month follow-up period will be based on TLFB data collected at each follow-up visit. Secondary outcomes will include mean daily alcohol consumption, %dCDT levels (change relative to baseline), and severity of alcohol-related problems (as measured on the SIP and number of DSM-IV AD criteria).

Efficacy analyses will be performed using linear mixed models implemented in SPSS. Medication group will be treated as a factor and treatment week as a continuous covariate. An interaction term between medication group and week will be used to evaluate the efficacy of dutasteride compared to placebo in reducing drinking behavior over time. Pretreatment drinking will be controlled for using TLFB drinking data for the month prior to screening as a covariate. Treatment goal (stop vs. reduce drinking) will also be included as baseline covariate. The robustness of results will be evaluated by running the model under three different conditions: 1) all provided information, 2) only completers, and 3) imputation where missing days are coded as HDDs for subjects who fail to complete treatment.

For aim 3, analysis of drinking outcome variables will be repeated by including genotype at the *AKR1C3* rs12529 polymorphism as an additional between-subject factor.

C.8.a.3 Examination of daily measures.

Multilevel models will be used to examine the relations among daily measures of mood, daily event triggers and the frequency of drinking and of heavy drinking (level 1 measures) and their moderation by medication (level 2 measure). To examine how the within-person processes vary across individuals (i.e., cross-level medication interactions), the level 1 parameters are considered as outcomes in the level 2 model. Of specific interest is how the level 1 slopes (e.g., the associations between mood or daily event triggers and heavy drinking) vary as a function of experimental condition (dutasteride vs. placebo). Control variables (baseline heavy drinking, depression symptom score, baseline AD symptom severity) will also be included in level 2 predictive models. The utility of each level 2 predictor will be determined by the significance tests of the level 2 partial regression slopes.

C.8.b. Sample size considerations:

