At the end of treatment week 12 (visit 8), subjects will complete a packet of questionnaires and be interviewed by research staff concerning their alcohol consumption and alcohol-related symptomatology (using the Alcohol section of the SCID-I, modified to ask about the past 30 days). Subjects will be compensated \$50 for this end-of-treatment visit. Subjects requesting additional treatment for alcohol problems will be referred to local treatment centers. For subjects who withdraw early and do not wish to continue with study visits/procedures, all end-of-treatment procedures will be administered at the time of withdrawal. Such subjects will also be invited to participate in-person or by telephone to provide Timeline Followback data at 2, 4, and 6-months post-treatment.

C.4.d. Visit 9, 10, and 11 (Post-treatment Assessment Visits): To evaluate the durability of treatment effects, patients will return to the clinic for post-treatment assessments 2,4, and 6-months after completion (or for early terminators, scheduled completion) of treatment. We will attempt to reach all subjects directly or via their locator. At this visit, the subject will complete the self-report packet of questionnaires and will be interviewed by the research staff. Blood samples for measurement of serum GGT, %dCDT and 3 α -diolG will be obtained. Subjects will be paid \$50 for the two and four month post treatment visit and \$75 for the six month post-treatment assessment visits. Subjects will be eligible to request drug assignment information after their 6-month post-treatment assessment.

C.5. Medical Management: The physician will meet with the subject at the beginning of treatment and will consult at least weekly with the study staff to monitor potential study related side effects and adverse event occurrence. The physician will evaluate the subject should severe or persistent adverse effects occur. At each treatment visit (2-7) subjects will receive brief counseling as part of medical management, which is described in detail below.

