Subsequent MM treatment sessions (15-20 minutes) will be conducted biweekly for the 12 weeks of active treatment. During these sessions, the study nurse will perform a review of the subject's general functioning, obtain vital signs, weight, BrAC and perform a brief assessment of the subject's drinking, monitor the subject's medication adherence, and make recommendations for the subject to follow until the next visit. For subjects who are not drinking at sensible levels, the recommendation will be made that they try different behavioral strategies for reducing drinking (e.g., spacing drinks, drinking drinks with lower alcohol content) that are outlined in the NIAAA Clinician's Guide (NIAAA 2007). Men who wish to reduce rather than stop drinking will be advised to consume not more than 4 standard drinks per day and 14 standard drinks per week. Because subjects will not be physically dependent on alcohol, reduction of heavy drinking is a safe and ethical goal.

Subject's receipt of other professional, self-help, or other treatments will be monitored during the study. Subjects will not be withdrawn from the study if they receive treatment outside the study, which in our experience with this population is relatively rare. However, we will monitor its occurrence and if group differences are found, a measure of additional treatment received will be incorporated in the data analysis.

C.6. Assessments:

C.6.a. Laboratory/Medical Assessments: A physical examination, urinalysis, urine toxicology, CBC, and a chemistry panel (which includes electrolytes, liver enzymes [ASAT, ALAT, GGT], bilirubin, BUN, and creatinine) will be used to screen subjects for medical exclusion criteria. Serum will be archived for HPLC measurement of carbohydrate deficient disialotransferrin (%dCDT; Clinical Neurobiology Laboratory, Medical Univ of S. Carolina) as a serum marker of heavy drinking. %dCDT is considered highly specific for heavy

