d. *Daily Events:* Participants will be asked whether they experienced a list of nine possible daily events (3 stressful, 3 pleasant, and 3 situations where someone might drink). These measures will be used to assess the influence of positive and negative events on drinking.

e. *Daily medication usage:* Using IVR, subjects will report daily medication use. Additionally, at each bi-weekly study visit, subjects will be asked by the study staff to indicate the number of study drug capsules taken each day. This method has been shown to be highly correlated with electronic monitoring of medication adherence (Feinn et al. 2003).

C.6.b.3. Areas assessed biweekly during the active treatment period and follow up visits:

a. *Alcohol use patterns:* The TLFB (Sobell and Sobell 1992) will be used to estimate drinking at intake, at each biweekly study visit during the active treatment period and at each of the two follow-up evaluations. This interview procedure will provide quantity/frequency of alcohol consumption data for each day during the period prior to the interview. We will also be collecting daily measures of alcohol consumption using IVR during the active treatment period because despite evidence of the reliability and validity of the TLFB when used by trained interviewers, the TLFB is less useful for detecting patterns of alcohol consumption that vary on a day-to-day basis (Carney et al. 1998; Searles et al. 2000). Daily IVR reports will also enable us to examine co-variation in daily mood and daily events with alcohol use in order to address whether dutasteride moderates associations between daily mood or daily events and drinking as our group has found using IVR methods for treatment with naltrexone (Kranzler et al. 2004; Armeli et al. 2006).

b. *Alcohol Craving:* The Penn Alcohol Craving Scale (PACS) is a 5-item self-report measure that includes questions regarding the frequency, intensity, and duration of craving over the past week as well (Flannery et al., 1999). The PACS has been shown to predict subsequent drinking during alcohol treatment trials (Flannery et al., 1999, 2003).

c. *Medication adverse effects:* Subjects will provide reports of side effects at each bi-weekly phone visit and study visit during the active treatment phase and 2-month follow-up visit using a list of adverse medication

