effects derived from prior studies of dutasteride (any ongoing potential medication side effects reported at the 2-month follow-up will be assessed again at 4- and 6-month follow-up visits as needed).

d. Measures of treatment received: Records of all medication taken will be recorded. The study staff will also record the number of contact hours subjects have been exposed to for any treatment outside of the study that is related to their drinking to identify if this variable might need to be considered as a covariate in outcomes analysis.

C.6.b.4. Areas assessed at intake, midpoint, end of treatment and at follow-up visits:

a. Alcohol-related problems: The Short Inventory of Problems (SIP). The SIP is a 15-item instrument derived from the Drinker Inventory of Consequences (DrInC), which was developed for use in Project MATCH as a measure of alcohol-related consequences.

b. Psychological symptoms: a) The Beck Depression Inventory (BDI), a 21-item self-report measure of depressive symptoms, yields a total score that ranges from 0 to 63 (Beck et al. 1961). The BDI is generally regarded as a sensitive self-report measure of depressive symptoms, and will be used to explore the relation between depressive symptoms and treatment. b) The State version of the Spielberger State-Trait Anxiety Inventory (STA), a 20-item self-report questionnaire (Spielberger 1983), will be used to provide concomitant monitoring of anxiety symptoms.

c. Drinking Motives: Drinking motives will be measured with the Drinking Motives Questionnaire [DMQ; (Cooper et al. 1992; Cooper 1994)] to explore potential changes as a result of treatment in drinking motives. This instrument contains 20 items with 4 subscales, drink to a) cope motives (e.g., "Because it helps when you are feeling nervous or depressed"), b) conformity motives (e.g., "Because it helps me fit in"), c) enhancement motives (e.g., "Because it's fun"), and d) social motives (e.g., "Because it makes a social occasion more enjoyable"). The DMQ will be administered at baseline and for those subjects who continue to drink again at midpoint, end of treatment and at the 2,4, and 6-month follow-up visits.

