E.7. Comparison of risks and anticipated benefits to patients and society: The risks associated with the counseling are minimal. Although the medication presents some risk, it has been shown to be safe when administered for benign prostatic hypertrophy for long periods of time (years). The potential risks of these treatments are minor compared to the risk incurred by individuals who continue to drink heavily. The risk/benefit ratio thus appears favorable to the proposed treatments.

E.8. Data and Safety Monitoring Plan (DSMP): The DSMP is established to ensure the safety of research participants and the integrity of the study data. [name], M.D., the principal investigator of this study, or one of the other study physicians, will be charged with the duty of determining the severity rating of adverse events. The study staff (P.I., co-investigators, clinical research coordinator) are responsible for collecting and recording all clinical data. As these results are collected, all toxicities and adverse events will be identified, graded for severity and assigned causality, reported to the required entities, and compiled for periodic review. After assigning causality, the P.I. will decide the course of action for the study participant. The P.I. will evaluate every adverse event and determine whether it affects the risk/benefit ratio of the study and whether modifications to the protocol or informed consent form are required. The principal investigator (and, in his absence, physician co-investigators) will differentiate serious from non-serious adverse events. Serious adverse events that are related to the study interventions and unexpected will be reported to the UCHC IRB and the NIAAA project officer within 48 hours. An annual report summarizing all adverse events will be prepared and reported to the NIAAA project officer. The following information will be considered in the periodic safety report:

- Number of patients who have completed the study.
- Dropout rates and reasons for the dropouts.
- Summary of adverse events.
- Any other relevant information

Adverse events during the treatment will be reported to the UCHC IRB, as well as to the NIAAA on an annual basis, with serious adverse events that are related to the study interventions and unexpected being reported within 48 hours. Any patients thought to be at risk from drinking or psychiatric or medical disorders during

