treatment or the follow-up period will be referred to services at UCHC or to other local health service providers. If it has been determined, for any reason, that the study should be suspended, we will discontinue enrollment of new patients, while continuing the treatment and monitoring of patients already enrolled in the study, unless to do so would create a risk that is not justified by any potential benefit to patients.

Women of Reproductive Age: As noted above women will not be included in this study as dutasteride is not FDA approved for use in women.

Data and Record Safety/Confidentiality: Records, filed in the IRB office, verify that all research project personnel have completed training in the protection of human research subjects in accordance with the guidelines of the U.S. Department of Health and Human Services (DHHS) and the Office for Human Research Protection (OHRP). The study staff (PI, Clinical research coordinator, etc.) will keep all study medical records containing personal identifiers in locked cabinets in a secure location. All electronic data and files (e.g., database, spreadsheet, etc.) containing identifiable patient information shall be password protected. Any computer hosting such files shall have a BIOS password to prevent access by un-authorized users. Furthermore, for systems not running Windows 2000/XP, a password-protected screen saver will be installed and configured to activate ten minutes after the computer has been idle. If patient data are to be exchanged with others, the data will be coded. If identification is necessary, then the data will be encrypted while en-route to the recipient with strong encryption levels (\geq 128 bits for symmetric encryption (DES) and \geq 1024 bits for asymmetric encryption (RSA)).

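### If the arms differ on outside alcohol treatment, C.5.a puts that post-randomisation variable into the analysis, without saying how or whether the adjusted result is primary

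*Combined protocol and SAP*

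**What the plan says.** C.5.a (Medical Management) keeps men who seek other help in the trial: "Subjects will not be withdrawn from the study if they receive treatment outside the study, which in our experience with this population is relatively rare". It then says that use will be monitored and that "if group differences are found, a measure of additional treatment received will be incorporated in the data analysis".

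C.6.b.3.d (Measures of treatment received) names the measure. Staff will "record the number of contact hours subjects have been exposed to for any treatment outside of the study that is related to their drinking", to see whether "this variable might need to be considered as a covariate in outcomes analysis". The heading over that item reads "Areas assessed biweekly during the active treatment period and follow up visits".

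Two passages bear on how outside treatment arises. E.8 arranges referral to local services for a group it describes as "Any patients thought to be at risk from drinking or psychiatric or medical disorders during" (the sentence goes on to name both study phases). In C.4.c, at the end-of-treatment visit, "Subjects requesting additional treatment for alcohol problems will be referred to local treatment centers".

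C.8.a.2 (Efficacy) does not mention outside treatment. Its two named covariates, pretreatment drinking and treatment goal, are both baseline variables. Its three robustness runs concern completers and missing days. It follows all men whether or not they continue treatment, and tests efficacy through the medication group by week interaction.

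**The concern.** Contact hours of outside treatment are not a baseline covariate. They accrue after randomisation, and E.8 makes drinking one of the reasons for referral. If dutasteride reduces drinking, fewer men on dutasteride may need other help, so a difference between the arms may be part of the drug's effect. Conditioning on it removes some of that effect, and it can also introduce confounding by whatever drives both drinking and help-seeking.

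Retaining men who take outside treatment, and following everyone, points to the total randomised effect as the target. The rule departs from that target only when the arms differ, which makes the final model depend on post-randomisation data. The text does not say what counts as a difference, how contact hours enter the model, which outcomes or period are affected, or whether the adjusted result replaces the main one. C.5.a says the measure *will* be incorporated; C.6.b.3.d says only that it *might* need to be considered.

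**Working it through.** **1. The plan's own figure.** C.8.b gives 80% power for d = 0.45 with 80 per arm at α = 0.05. Two-sided: 0.45 × √(80/2) = 2.846; 2.846 − 1.960 = 0.886; Φ(0.886) = 81.2% (80.8% with the t distribution). The figure reproduces.

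**2. The trigger is undefined, and its definition matters.** Suppose uptake is 10% v 20% (assumed). The null SE is √(2 × 0.15 × 0.85/80) = 0.0565 and the alternative SE is √((0.09 + 0.16)/80) = 0.0559. The chance of triggering is about Φ((0.10 − z × 0.0565)/0.0559):
- trigger at 0.05: 42%
- trigger at 0.10: 55%
- trigger at 0.20: 69%

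**3. Why level comparisons move.** In a linear model, adjusted effect = unadjusted effect − γ × (arm difference in mean outside treatment), where γ is the fitted coefficient of outside treatment. If heavier drinkers seek more help, γ is positive and the drug effect shrinks.

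**4. Size when the drug acts on uptake only through drinking.** The documents give no rate of use, so every input here is assumed: placebo use 5–30%, odds of use rising 2–5 fold per SD of drinking, d = 0.45, 80 per arm, contact hours as a subject-level covariate, trigger p < 0.05, 20,000 simulated trials per setting. The outcome's correlation with earlier drinking is 0.7 at odds ratios 2 and 3, and 0.9 at 5, so the top of the range combines two assumptions. With outside treatment having no effect on drinking:

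| Placebo use | Odds ratio | Trigger fires | Shift when fired | Shift averaged over trials |
|---|---|---|---|---|
| 5% | 2 / 3 / 5 | 0.058 / 0.072 / 0.094 | −3.8 / −6.8 / −11.7% | −0.2 / −0.5 / −1.2% |
| 10% | 2 / 3 / 5 | 0.078 / 0.113 / 0.156 | −5.8 / −9.0 / −15.0% | −0.5 / −1.1 / −2.7% |
| 20% | 2 / 3 / 5 | 0.106 / 0.167 / 0.236 | −7.3 / −11.3 / −18.0% | −0.9 / −2.1 / −5.0% |
| 30% | 2 / 3 / 5 | 0.128 / 0.207 / 0.303 | −8.0 / −11.7 / −18.9% | −1.2 / −2.8 / −6.8% |

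Power becomes 77.3–80.6%. If outside treatment lowers drinking by 0.5 SD, the shift when fired is +1% to −12%, and averaged it is +0.2% to −3.9%. A separate run at 10–20% use and odds ratio 3 gave 10–12% when fired and about 1.5–2.5% averaged. With no drug effect, type I error is 4.7–5.0%. If the drug does not change use at all, the averaged shift is nil.

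**5. Size when the drug changes uptake directly.** Assumed: 20% baseline chance of use, log-odds lowered by 1.0 on drug, a severity factor driving both use and drinking, no effect of outside treatment on drinking, yes/no covariate, 4,000 trials. The trigger fires in 53.5% of trials. In those, the estimate goes from 0.472 to 0.398, a loss of 0.074. Averaged, 0.535 × 0.074 = 0.040, so 0.449 falls to 0.409 (0.040/0.449 = 9%). Power falls from 80.3% to 72.5%; a separate run gave about 69%. With no drug effect on drinking, the rule produces a bias of +0.039 SD, against the drug, and rejection of 6.2% v 5.2% unadjusted. Other runs gave biases of about +0.02 to +0.05 and rejection near 5%.

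**6. Group by week.** A subject-level main effect does not vary with week. In 200 data sets of 160 men over 12 weeks it changed the interaction estimate by at most 8 × 10⁻¹⁷ with complete data, and by 0.013 SE with 16 dropouts. A time-varying term is also open, since the measure is listed as biweekly. In 1,000 trials per setting (use about 5–24%) it moved the slope difference by under 1% if outside treatment had no effect on drinking. If it lowered drinking by 0.5 units, the slope difference moved +3% to +17% when fired, with firing in 3–8% of trials.

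**The case against.** The strongest reply is that this is a small wording gap. C.5.a expects outside use to be relatively rare, so the 5–10% rows apply, where the averaged shift is 0.2–2.7%. C.6.b.3.d does name a measure and a covariate role. C.5.a does not say that the adjusted run replaces the main model, and C.8.a.2 leaves the variable out, so a supplementary analysis would fit all three sections. Most of this stands and limits the size of the point. It does not remove it: C.5.a is worded as a commitment, and no section gives the adjusted run supplementary status.

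Several stronger readings are tempting but unsupported:
- *The main efficacy contrast is biased.* Not with a subject-level term and complete data (step 6).
- *The rule inflates false positives.* Not if the drug alters use only through drinking. With a direct effect on uptake there is a small bias, and rejection is between about 5% and 6.2%.
- *The protocol makes outside treatment purely a consequence of drinking.* E.8 also covers psychiatric and medical disorders. The C.4.c referral comes at the end-of-treatment visit, so it bears only on follow-up.
- *Aim 2 is certainly affected.* Collection of contact hours at follow-up rests on the C.6.b.3 heading. Table 1 has no row for it, and the side-effect item under the same heading has its own schedule.

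**Conclusion.** The concern holds and is modest. As written, C.5.a requires a data-dependent adjustment for a post-randomisation variable, which changes the target in just those trials where the drug may have altered the need for other care. What is exposed is comparison of level: the two percentage outcomes, the secondary scores, and Aim 2 levels if contact hours are recorded at follow-up. C.8.a.2 gives no separate model for the percentage outcomes, so that scope is partly inferred. Contact hours as a subject-level term cost roughly 4–19% of the level difference when the trigger fires (outside treatment without effect on drinking), and usually under 3% averaged over trials at low use. Losses are larger if the drug changes uptake directly. The sizes rest on assumed inputs, because the protocol gives no rate; the direction can change if outside treatment itself lowers drinking. The sponsor should make the change because it is nearly free. The referrals are not in question.

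A separate, minor point: age, *AKR1C3* genotype, number of AD criteria and psychiatric medication are urn variables in C.3.c but are not in the main C.8.a.2 model (genotype enters only for Aim 3). A reader might infer bias; there is none in the linear estimate. If these variables explain an assumed 2–10% of residual variance, power for a level comparison at d = 0.45 would be 81.5–84.7% instead of 80.8% (at 10%, effective d = 0.45/√0.90 = 0.474). As main effects they do nothing for group by week.

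**What to change.** In C.5.a, delete the conditional trigger, and align C.6.b.3.d with it. In C.8.a.2, state that:
- outside treatment (any use, and contact hours) will be summarised by arm, separately for the 12 weeks and for follow-up;
- it does not enter the primary model;
- any adjustment is one labelled sensitivity analysis, run whatever the arm difference, with the outcomes, the period and the form of the term given (subject total or time-varying);
- that analysis does not estimate the total randomised effect.

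Separately, prespecify the C.3.c urn variables as baseline covariates in C.8.a.2, regardless of observed imbalance, and reconcile the longer urn list in C.3.c with the shorter one in C.4.b.

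The cost is analysis-plan wording, with no new data and no change in sample size. The separate point adds about four model terms against 160–176 men.
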